ABBREVIATIONS

Abbreviation Explanation

AAO-HNS American Academy of Otolaryngology - Head and Neck Surgery

AE Adverse Event

BCA Bone Conduction Average

C Celsius

CRF/eCRF Case Report Form/electronic Case Report Form

CRO Contract Research Organization

C-SSRS Columbia-Suicide Severity Rating Scale

dB Decibel

EDC Electronic Data Capture System

F Fahrenheit FAX Facsimile

FDA Food and Drug Administration

GCP Good Clinical Practice

HIPAA Health Insurance Portability and Accountability Act

Hz Hertz

ICH International Conference on Harmonization

IT Intratympanic

MedDRA Medical Dictionary for Regulatory Activities

mL Milliliter
mg Milligram
mm Millimeter

OTO-104 Investigational Product

PTA Pure Tone Average

REC Research Ethics Committee

SAE Serious Adverse Event SAP Statistical Analysis Plan

SOC System Organ Class

TEAE Treatment Emergent Adverse Event

SYNOPSIS

NAME OF SPONSOR/COMPANY: Otonomy, Inc.

NAME OF INVESTIGATIONAL PRODUCT: OTO-104

NAME OF ACTIVE INGREDIENT: Dexamethasone

Title of Study: A 6-month, multicenter, Phase 3, open-label extension safety study of OTO-104 given at 3-month intervals by intratympanic injection in subjects with unilateral Meniere's disease.

Study Center(s): This study will be conducted at approximately 60-70 sites in six countries in the European Union, including United Kingdom, Germany, Poland, Italy, Belgium and France.

Studied Period: 18 months Phase of Development: Phase 3

Study Design:

This is a 6-month, multicenter, Phase 3, open-label extension safety study in subjects with unilateral Meniere's disease. Subjects will receive 1 intratympanic (IT) injection of 12 mg OTO-104 at 3-month intervals for a total of 2 injections. Safety data to be collected include adverse events, concomitant medications, otoscopy, vital signs, audiology, tympanometry, Columbia-Suicide Severity Rating Scale (C-SSRS) questionnaire and a Meniere's disease symptom questionnaire.

Objective:

The objective is to assess the safety of repeat IT injections of 12 mg OTO-104 at 3-month intervals in an open-label study.

Methodology:

The duration of the study for each subject will be 6 months.

Once subjects meet all eligibility criteria, they will be enrolled and may receive up to 2 IT injections of OTO-104 at 3-month intervals. All subjects will remain on standard of care treatment for unilateral Meniere's disease. Subjects will return to the study sites at Month 3 for safety assessments and another IT injection of OTO-104. Safety assessments will be completed at the end of the study (Month 6) or upon early withdrawal from the study.

Number of Subjects:

Up to 300 subjects will be enrolled.

Diagnosis and Main Criteria for Inclusion:

Subjects enrolled in the study will have unilateral Meniere's disease as outlined by the American Academy of Otolaryngology - Head and Neck Surgery (AAO-HNS) Committee on Hearing and Equilibrium in 1995 (Committee on Hearing and Equilibrium, 1995).

To be eligible for this study, each of the following criteria must be satisfied with a "YES" answer (unless not applicable):

- 1. Subject is a male or female aged 18 years or older.
- 2. Subject has completed the Phase 2 (104-201403) or Phase 3 (104-201508) clinical study.
- 3. Female subjects of childbearing potential [i.e., not surgically sterile and/or not post-

menopausal (≥12 months since last menstrual period and 45 years of age or older)] must have a negative urine pregnancy test before enrollment. Women of childbearing potential who are not abstinent from sex with male partners may be entered into the study if they are using and willing to continue to use highly effective or "double barrier" contraceptive precautions for the duration of the study (e.g., oral contraceptives, contraceptive implant or injection, intrauterine device, or "double barrier" methods including condom with diaphragm, male condom with cervical cap, male condom with spermicide, or diaphragm and spermicide).

- 4. Subject is willing to comply with the protocol and attend all study visits.
- 5. Subject is able to provide written informed consent, including agreement to local privacy language requirements either within the informed consent or in ancillary documents compliant with local privacy laws before the initiation of any study-related procedures.

Diagnosis and Main Criteria for Exclusion:

To be eligible for this study, each of the following criteria must be satisfied with a "NO" answer: (unless not applicable):

- 1. Subject has an infection in the ear, sinuses, or upper respiratory system.
- 2. Subject is pregnant or lactating.
- 3. Subject has a history of immunodeficiency disease.
- Subject has active or recent (<1 month prior to screening) middle ear disease, including but not limited to: chronic otitis media, acute otitis media, middle ear effusions, middle ear atelectasis, or cholesteatoma.
- 5. Subject has an abnormality of the tympanic membrane in the affected ear that would increase the risk associated with intratympanic injection including but not limited to a monomeric, atelectatic or atrophic tympanic membrane.
- 6. Subject has a history of tympanostomy tubes that includes evidence of perforation or lack of closure.
- 7. Subject has a history of previous endolymphatic sac surgery.
- 8. Subject has a history of previous use of intratympanic gentamicin in the affected ear.
- 9. Subject has history of drop attacks.
- 10. Subject has used systemic steroids within 1 month prior to Visit 1.
- 11. Subject has had intratympanic steroids within 1 month prior to Visit 1.
- 12. Subject has experienced an adverse reaction to intratympanic injection of steroids.
- 13. Subject has a hypersensitivity to dexamethasone or any of the excipients in OTO-104.
- 14. Subject has any other clinically significant illness or medical condition that, in the investigator's and the medical monitor's opinion, would prohibit the subject from participating in the study.
- 15. Subject has participated in a clinical trial within 30 days of Visit 1, not including the OTO-104 Phase 3 study (104-201508).

Criteria for Evaluation:

Safety Evaluations:

Key safety assessments include:

- Adverse events
- Audiometry assessments
- Tympanometry
- Local tolerability (otoscopic examinations)
- Vital sign measurements
- Columbia-Suicide Severity Rating Scale (C-SSRS): Baseline and Since Last Visit versions

Other Evaluations:

• Meniere's symptom questionnaire

Statistical Methods:

This is an open label safety study with one treatment group. All statistical analyses will be descriptive in nature.

Investigational Product, Dosage and Mode of Administration:

OTO-104 12 mg, single, intratympanic injection, 0.2 mL

Duration of Treatment:

Single IT injection given at Day 1 and Month 3

Reference Therapy, Dosage and Mode of Administration:

None

Time and Events Schedule: See Table 1.

Table 1: Time and Events Table

	Screening/ Baseline/Dose No. 1	Follow-up/ Dose No. 2	End-of-Study/ Early Term.	Unscheduled Visit
	Visit 1	Visit 2	Visit 3 ²	Unscheduled
Procedure	Day 1	Month 3 (± 2 weeks)	Month 6 (± 2 weeks)	N/A
Informed consent (including privacy language/documents)	X			
Eligibility criteria	X			
Medical history ³	X			
Concomitant medications	X	X	X	X
Vital sign measurements ⁴	X	X	X	X
Height and weight measurements	X		X ⁵	
Urine Pregnancy test ⁶	X	X	X	
Tympanometry	X	X	X	X as indicated
Audiometry	X	X	X	X as indicated
Otoscopy	X	X	X	X
C-SSRS assessment	X	X	X	X
Meniere's symptom questionnaire	X	X	X	
Administer study drug	X	X		
Adverse event monitoring	X	X	X	X

¹ Visit 1 may also be the last study visit for 104-201508.

² Procedures scheduled for Visit 3 will be performed at the end of the follow-up period (± 2 weeks) or upon early discontinuation from the study.

³ Medical history to include information on demographics.

⁴ Vital sign measurements include blood pressure and pulse rate.

⁵ Only weight will be taken at Study Visit 3.

[figure not shown]
⁶ Female subjects of childbearing potential will have a urine pregnancy test via dipstick at every scheduled visit. On Visit 1 and 2, the pregnancy test must be completed and confirmed negative prior to dosing. If a subject is found to be pregnant after dosing with OTO-104, they will complete the follow-up period but will not be dosed further with OTO-104.

At Visit 1, the Since Last Visit version of the C-SSRS will be used for subjects enrolling from Study 104-201508 while the Baseline version will be used for all subjects enrolling from Study 104-201403. The Since Last Visit version of the C-SSRS will be used at all subsequent visits.

1. BACKGROUND

Meniere's disease is an idiopathic syndrome of endolymphatic hydrops (Committee on Hearing and Equilibrium, 1995). It is associated with a distinct pattern of clinical symptoms comprised of vertigo, hearing loss, tinnitus and aural fullness. It is more frequently unilateral than bilateral. Episodic vertigo is considered the most prominent symptom, with episodes typically lasting at least 20 minutes and resulting in significant patient morbidity. The diagnosis is primarily a clinical one, since there are no specific diagnostic tests for Meniere's disease. The disease is known to wax and wane, but eventually results in irreversible sensorineural hearing loss at all frequencies in the affected ear. While the pathogenesis of Meniere's disease has not been elucidated, one well-accepted mechanism involves the dysregulation of labyrinth fluid volume/ion balance resulting in endolymphatic hydrops (Shea, 1993). The increase in fluid volume and consequent increased labyrinth pressure may then be expressed as the Meniere's spectrum of symptoms.

There is no cure for Meniere's disease. Treatment tends to focus on relieving the vertigo symptoms, where it is hypothesized that reducing inner ear fluid volume will relieve the hydrops and associated clinical picture. It is for this reason that many subjects are initially started on low salt diets and diuretics (Barritt, 2008). A number of medical systemic treatments are also used to relieve Meniere's disease symptoms, including but not limited to antihistamines, anticholinergics, phenothiazines, benzodiazepines, and corticosteroids; however, these interventions are often inadequate in relieving the symptoms of Meniere's disease. A device that generates low-pressure pulses, the Meniett® device, is indicated for the symptomatic treatment of Meniere's disease. However, the device is not widely used and is not currently considered standard of care (Kim et al, 2005). Surgical decompression may be attempted in severe cases unresponsive to medical intervention, but surgical outcomes are frequently unsatisfactory. Finally, patients with unresponsive disease may undergo chemical or surgical neuroablation, resulting in symptom relief at the cost of destruction of the 8th cranial nerve. Thus, there continues to be an unmet medical need for therapies to address this debilitating disease.

1.1. Rationale for Safety Study

Two clinical studies have been completed in the United States: a Phase 1b study and a Phase 2b study. In addition, three studies have been initiated in either the United States or the United Kingdom: Phase 2 repeat dose safety study, Phase 3 study and Phase 3 extension study. The randomized, placebo-controlled, double-blind, multi-center Phase 2b study in 154 unilateral Meniere's disease patients demonstrated that a single IT administration of OTO-104 resulted in improvements in vertigo control. The completed and ongoing clinical studies have been either single-dose with a 3-month or 4-month follow-up period or a repeat-dose with 4 doses administered over one year. Because Meniere's disease is chronic and intermittent, the safety of repeat administration needs to be evaluated. This study was designed with a two injection design to look at repeat doses over the course of six months. Three months was chosen as the dose interval due to information gained during the follow-up period in regard to effect and safety in the completed Phase 1b and Phase 2b studies.

2. OBJECTIVES

The objective is to assess the safety of repeat IT injections of 12 mg OTO-104 at 3-month intervals in an open-label study in subjects with unilateral Meniere's disease.

3. OVERVIEW OF STUDY DESIGN

This is a 6-month, multicenter, Phase 3, open-label extension safety study in subjects with unilateral Meniere's disease. Subjects will receive 1 IT injection of 12 mg OTO-104 at 3-month intervals for a total of 2 injections. Safety data to be collected include adverse events, concomitant medications, otoscopy, vital signs, audiology, tympanometry, Columbia-Suicide Severity Rating Scale (C-SSRS) questionnaire and a Meniere's disease symptom questionnaire.

Once subjects meet all eligibility criteria, they will be enrolled and may receive up to 2 IT injections of OTO-104 at 3-month intervals. All subjects will remain on standard of care treatment for unilateral Meniere's disease. Subjects will return to the study sites at Month 3 for safety assessments and another IT injection of OTO-104. Safety assessments will be completed at the end of the study (Month 6) or upon early withdrawal from the study.

4. STUDY POPULATION

4.1. General Considerations

Up to 300 subjects will be enrolled at approximately 60-70 sites in six countries, including United Kingdom, Germany, Poland, Italy, Belgium and France. Subjects will be enrolled only if they meet all of the inclusion criteria and none of the exclusion criteria

4.2. Inclusion Criteria

Subjects enrolled in the study will have unilateral Meniere's disease as outlined by the American Academy of Otolaryngology - Head and Neck Surgery (AAO-HNS) Committee on Hearing and Equilibrium in 1995 (Committee on Hearing and Equilibrium, 1995).

To be eligible for this study, each of the following criteria must be satisfied with a "YES" answer (unless not applicable):

- 1. Subject is a male or female aged 18 years or older.
- 2. Subject has completed the Phase 2 (104-201403) or Phase 3 (104-201508) clinical study.
- 3. Female subjects of childbearing potential [i.e., not surgically sterile and/or not postmenopausal (12 months since last menstrual period and 45 years of age or older)] must have a negative urine pregnancy test before enrollment. Women of childbearing potential who are not abstinent from sex with male partners may be entered into the study if they are using and willing to continue to use highly effective or "double barrier" contraceptive precautions for the duration of the study (e.g., oral contraceptives, contraceptive implant or injection, intrauterine device, or "double barrier" methods including condom with diaphragm, male condom with cervical cap, male condom with spermicide, or diaphragm and spermicide).
- 4. Subject is willing to comply with the protocol and attend all study visits.
- 5. Subject is able to provide written informed consent, including agreement to local privacy language requirements either within the informed consent or in ancillary documents compliant with local privacy laws before the initiation of any study-related procedures.

4.3. Exclusion Criteria

To be eligible for this study, each of the following criteria must be satisfied with a "NO" answer: (unless not applicable):

- 1. Subject has an infection in the ear, sinuses, or upper respiratory system.
- 2. Subject is pregnant or lactating.
- 3. Subject has a history of immunodeficiency disease.
- 4. Subject has active or recent (<1 month prior to screening) middle ear disease, including but not limited to: chronic otitis media, acute otitis media, middle ear effusions, middle ear atelectasis, or cholesteatoma.

- 5. Subject has an abnormality of the tympanic membrane in the affected ear that would increase the risk associated with intratympanic injection including but not limited to a monomeric, at electatic or atrophic tympanic membrane.
- 6. Subject has a history of tympanostomy tubes that includes evidence of perforation or lack of closure.
- 7. Subject has a history of previous endolymphatic sac surgery.
- 8. Subject has a history of previous use of intratympanic gentamicin in the affected ear.
- 9. Subject has history of drop attacks.
- 10. Subject has used systemic steroids within 1 month prior to Visit 1.
- 11. Subject has had intratympanic steroids within 1 month prior to Visit 1.
- 12. Subject has experienced an adverse reaction to intratympanic injection of steroids.
- 13. Subject has a hypersensitivity to dexamethasone or any of the excipients in OTO-104.
- 14. Subject has any other clinically significant illness or medical condition that, in the investigator's and the medical monitor's opinion, would prohibit the subject from participating in the study.
- 15. Subject has participated in a clinical trial within 30 days of Visit 1, not including the OTO-104 Phase 3 study (104-201508).

5. RANDOMIZATION AND BLINDING

This study is an open-label study with all subjects receiving OTO-104; therefore, no randomization or blinding is required.

5.1. Enrollment Procedures

5.1.1. Assignment of Subject Identification Numbers

All subjects will retain the same unique subject identification number as the one assigned in clinical study 104-201403 or 104-201508 plus a 3-digit number to indicate which study the subject participated in previously. The subject identification number will be used to identify the subject throughout the study and will remain with the subject throughout the duration of the study. All subjects with a signed informed consent for the study, whether enrolled or not (screen failures, subject refusal, etc.), will be documented.

6. DOSAGE AND ADMINISTRATION

6.1. Study Drug Administration

OTO-104 12 mg will be administered as a single, 0.2 mL intratympanic injection of 60 mg/mL OTO-104. The recommended injection procedure for intratympanic administration of OTO-104 in Meniere's disease subjects is as follows:

- 1. Place the subject in a recumbent position with the treated ear upwards. Anesthetize the tympanic membrane by covering the external surface of the posterior inferior quadrant with topical lidocaine/prilocaine cream (i.e., _______) until the tympanic membrane is numb. If applicable, suction away the topical lidocaine/prilocaine cream.
- 2. Using the 1 mL syringe pre-loaded with OTO-104 and equipped with a 25 or 26 gauge needle, insert the needle through the tympanic membrane with the bevel facing in an inferoposterior direction to a depth of approximately 2-3 mm just inferior to the round window niche, and with firm but gentle pressure, inject 0.2 mL taking care not to insert the needle further than necessary. Use of this technique will minimize the possibility of OTO-104 adhering to the underside of the tympanic membrane. Do not incise the tympanic membrane to form a ventilation hole as this is not needed due to the small injection volume.

6.2. Compliance

OTO-104 will be administered by site personnel as a single, intratympanic injection at Visit 1 and 2 except when withheld due to potential safety concerns. Any deviations in administration will be documented in the source documents and the eCRF.

The site will maintain a log of all study drug dispensed and returned. Drug supplies for each subject will be inventoried and accounted for throughout the trial.

7. PRIOR, CONCOMITANT, AND SUBSEQUENT THERAPY

Use of all concomitant medications will be recorded in the subject's eCRF. This will include all symptomatic relief medications for Meniere's disease symptoms, prescription drugs, herbal products, vitamins, minerals, and over-the-counter medications taken within 30 days before enrollment, which will be considered prior therapy. Any concomitant medication deemed necessary for the welfare of the subject during the study may be given at the discretion of the Investigator except for those listed in Section 7.1. Any changes in concomitant medications will be recorded in the subject's eCRF.

7.1. Proscribed Therapy or Procedures During the Study Period

The following therapies are prohibited during the study:

- Systemic corticosteroids
- Immunosuppressive medications
- Phenol for use in anesthetizing the tympanic membrane
- Intratympanic injection other than that outlined in the current study
- Surgery for treatment of Meniere's disease
- Other investigational drug(s) or device(s)

Use of any of these proscribed therapies will be considered a protocol deviation.

7.2. Symptomatic Relief Medications

It is recognized that subjects may at times use certain medications for relief of symptoms related to Meniere's disease during the course of the study. Intermittent use of vestibular suppressants and anti-emetics is allowed as symptomatic relief medications. The use of gentamicin, corticosteroids or surgery at any time during the study will be considered a protocol deviation. Any changes reported by the subjects in concomitant medications should be recorded in the subject's eCRF.

8. STUDY EVALUATIONS

8.1. Study Procedures by Visit

8.1.1. Visit 1: Day 1 (Screening/Baseline/Dose No. 1)

The following assessments will be performed at Visit 1. For subjects enrolling directly (within 1 month) from Study 104-201508, the tympanometry, audiometry, otoscopy and C-SSRS assessment data collected at the final visit of Study 104-201508 will serve as the Baseline data for Visit 1.

The following assessments will be performed at Visit 1.

- Informed consent
- · Confirm eligibility criteria
- Medical history
- Concomitant medications
- Vital signs
- Height and weight measurements
- Urine pregnancy test (for female subjects of childbearing potential only)
- Tympanometry
- Audiometry
- Otoscopy
- C-SSRS assessment: Baseline version or Since Last Visit version
- Meniere's symptom questionnaire
- Administer OTO-104 (all assessments in the above list must be conducted prior to OTO-104 administration)
- Adverse events (to be collected during or after OTO-104 administration)

8.1.2. Visit 2: Month 3 (± 2 weeks) (Follow Up and Dose No. 2)

The following assessments will be performed at Visit 2.

- Concomitant medications
- Vital signs
- Urine pregnancy test (for female subjects of childbearing potential only)
- Audiometry
- Tympanometry
- Otoscopy
- C-SSRS assessment, Since Last Visit version
- Meniere's symptom questionnaire
- Administer OTO-104 (all assessments in the above list must be conducted prior to OTO-104 administration)
- Adverse events (to be collected during or after OTO-104 administration)

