9. ADVERSE EVENT (AE) REPORTING

Timely, accurate, and complete reporting and analysis of safety information from clinical trials will be conducted in accordance with Good Clinical Practice.

All AEs, including SAEs reported or observed during or after dosing with the study drug will be recorded on the AE page of the eCRF for all enrolled subjects. Information to be collected includes description of event, date of onset, investigator-specified assessment of the severity and relationship to study drug, date of resolution of the event, seriousness, any required treatment or evaluations, and outcome. Adverse events resulting from concurrent illnesses, reactions to concurrent illnesses, reactions to concurrent medications, or progression of disease states must also be reported. Perforations of the tympanic membrane will be captured as AEs only if the perforation increases in size and does not resolve by the end of the study.

If the existing medical condition worsens at any time after application of study drug, it should be recorded as an AE.

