11.7.1. Adverse Events

Version 18.1 of Medical Dictionary for Regulatory Activities (MedDRA) will be used to code all AEs.

The primary analysis of AEs will consider only treatment emergent AEs (TEAEs), events occurring for the first time, or worsening during or after the first dose of study drug. Subject incidence of TEAEs and SAEs will be tabulated by preferred terms and system organ class. These analyses may also be tabulated by visit, time of onset and/or cumulative exposure. In addition, severity and relationship to study drug will also be presented. Adverse events will be presented by descending order of frequency in MedDRA system organ class and preferred term.

Subgroup analyses of AEs by gender will be examined. Listings of all SAEs, AEs leading to study withdrawal, and deaths on-study will also be included. Duration and outcome of each AE will be reported in subject listings.

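### At Visit 2 adverse events are listed only after the second injection, so non-serious events from the 11 to 15 weeks after dose 1 need not be asked about before re-dosing

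*Combined protocol and SAP*

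**What the plan says.** Section 8.1.2 lists concomitant medications, vital signs, urine pregnancy test, audiometry, tympanometry, otoscopy, C-SSRS and the Meniere's symptom questionnaire. The dosing item follows, with the instruction that "all assessments in the above list must be conducted prior to OTO-104 administration". Adverse events come after that, with their own timing note: "Adverse events (to be collected during or after OTO-104 administration"). Section 8.1.1 uses the same two instructions at Visit 1. Sections 8.1.3 (Visit 3) and 8.1.4 (unscheduled visit) list adverse events with no timing note.

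Section 6.2 has the drug given at both dosing visits "except when withheld due to potential safety concerns". Section 3 describes the next scheduled contact after Day 1: "Subjects will return to the study sites at Month 3 for safety assessments and another IT injection of OTO-104". Table 1 schedules nothing between Day 1 and Month 3.

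The general rule in section 9 is "All AEs, including SAEs reported or observed during or after dosing with the study drug will be recorded on the AE page". Section 9.2.1 relies on spontaneous reports or an open question about health since the last visit. Neither section says whether that question comes before or after dose 2. On analysis, section 11.7.1 says "These analyses may also be tabulated by visit, time of onset and/or cumulative exposure".

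**The concern.** At Visit 1 the timing note is harmless, because no study drug has yet been given in this study. At Visit 2 the same words cover a visit at which the subject has already been exposed for about three months. A site that works down the list asks about those months after injecting again.

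Two things are at stake.

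- **The dosing decision.** Section 6.2 presupposes that safety concerns are known before the syringe is used, and section 10.2 lets the investigator discontinue a subject for an intolerable event. Exclusion criterion 12 treats an earlier adverse reaction to intratympanic steroids as relevant to entry, but Table 1 checks eligibility only at Visit 1. At Visit 2, therefore, what is known about a symptomatic reaction to dose 1 depends largely on asking about adverse events.
- **Attribution.** The only objective is the safety of repeat injections, and section 9.1.2 rests causality largely on timing. If events after dose 1 are first elicited after dose 2, those that began on the day of dose 2, or whose onset date is incomplete, are harder to assign to one dose.

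**Working it through.** **1. Length of the period.** The input is the Visit 2 heading, "8.1.2. Visit 2: Month 3 (± 2 weeks) (Follow Up and Dose No. 2"). The documents do not define a month in days, so several conventions are shown. The formula is days ÷ 7, then ± 2 weeks.

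| Three months taken as | Nominal weeks | Window (weeks) |
|---|---|---|
| 365.25 ÷ 4 = 91.3 days | 13.04 | 11.04 to 15.04 |
| 90 days | 12.86 | 10.86 to 14.86 |
| 13 weeks (91 days) | 13.00 | 11.00 to 15.00 |
| 92 days (longest calendar case) | 13.14 | 11.14 to 15.14 |
| 12 weeks (4-week months) | 12.00 | 10.00 to 14.00 |

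Under calendar months the period is 11 to 15 weeks. The plan states no figure of its own to reproduce.

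**2. The four visit lists side by side.**

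| Visit | Dose given? | Timing note on adverse events | Events from earlier study dosing possible? |
|---|---|---|---|
| Visit 1 (8.1.1) | Yes | During or after dosing | No |
| Visit 2 (8.1.2) | Yes | During or after dosing | Yes |
| Visit 3 (8.1.3) | No | None | Yes |
| Unscheduled (8.1.4) | No | None | Yes |

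The note appears only where an injection is given, so its natural referent is that visit's injection. At Visit 2 this leaves events since dose 1 without a stated place before dosing.

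**3. Does another section supply the missing step?** Section 6.2 does not mention asking about adverse events. Sections 9 and 9.2.1 require events to be recorded but do not place the question relative to dose 2. Table 1 marks adverse event monitoring at Visit 2 with no timing. By contrast, where a check must come before dosing the protocol says so: section 8.2.2 and a Table 1 footnote require a negative pregnancy test before the injection at both dosing visits.

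**4. What is already known before dose 2.**

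- Otoscopy: ear canal, tympanic membrane and healing of the injection site.
- Audiometry and tympanometry: hearing and middle-ear function.
- Symptom questionnaire: vertigo, tinnitus, ear fullness and hearing difficulty.
- C-SSRS: suicidality since the last visit, with its own AE and SAE rules in section 8.2.6.
- Concomitant medications: new treatments, which may point to an event.
- Vital signs.
- Serious events: reported within 24 hours, whatever the visit schedule (section 9.2.2).
- Events already reported at an unscheduled visit, or volunteered by the subject.

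The remainder is non-serious events that none of these brings out.

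**5. Effect on the analysis.** Date of onset is collected for every event (sections 9 and 9.2.1). The primary AE analysis counts treatment-emergent events from the first dose, so the order of questions around dose 2 does not change which events it includes. Only the optional tabulations by visit, onset or cumulative exposure, and the investigator's causality rating, depend on separating the two doses. Within those, the difficulty is confined to same-day or partial onset dates.

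**The case against.** The strongest reply is that the phrase marks when AE capture starts and is not an instruction to delay the question. Sections 9 and 11.7.1 use the same expression in that sense, and by Visit 2 every event since dose 1 already falls after administration of study drug. The order of the list may also be mere layout: tympanometry and audiometry swap places between Visits 1 and 2, and adverse events come last at Visit 3 and at unscheduled visits, where nothing is injected. Nothing forbids asking first.

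Much of this stands. The phrase was probably carried over from Visit 1, and many sites may well ask before injecting. But permission is not a requirement. The one ordering rule in the list covers only the items above the dosing line, and adverse events are not among them.

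The objection on data quality also largely stands. Asking a few minutes earlier hardly changes recall over three months, and recorded onset dates already separate most events.

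A reader might go further and infer that section 6.2 cannot work, that data on dose 1 are lost, or that a countable number of subjects would be re-injected despite a relevant event. The documents support none of these. The other pre-dose checks do inform section 6.2, events are still recorded with their dates, and no rate is given from which a count could be derived. The 300 subjects in section 11.1 are an enrolment ceiling, not the number who will receive dose 2.

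**Conclusion.** The point holds in a limited form. Section 8.1.2 as written does not require a site to ask about non-serious events from the 11 to 15 weeks after dose 1 before giving dose 2, and no other section fills that gap. It concerns any subject who receives dose 2. The affected events are those that the other pre-dose assessments do not reveal, that were not reported earlier, and that the subject does not volunteer. Their number cannot be estimated from the documents.

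The conclusion assumes calendar months for the interval and takes the timing note to refer to the injection at that visit. If it was meant to cover any time since first dosing, the problem is ambiguous wording, and the same edit cures it. The eCRF and its completion guidelines were not available and may already address the timing. The change is worth making because repeat-dose safety is the study's only objective and the edit costs very little.

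**What to change.** Reconcile sections 6.2, 8.1.2, 9.2.1 and Table 1 on when events since the last visit are elicited relative to dose 2. The simplest way is to split the Visit 2 item in two:

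- *adverse events since last visit*, listed with the pre-dose assessments;
- *adverse events during or after administration*, kept below the dosing line.

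Table 1 needs a matching footnote. Where an onset falls on the day of dose 2, or the onset date is partial, the eCRF should record whether the event began before or after that injection; for other events the onset date is enough.

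The cost is one line of protocol text, the footnote and a minor eCRF clarification, with no added visit or procedure. No criterion for withholding a dose is proposed; that remains for the sponsor and investigators.
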